### 12.3. Treatment of Missing and Spurious Data

Spurious data, which were not clarified by the query process before CDMS closure, are indicated. If appropriate, descriptive and inferential analyses are performed both with /without such data.

### 12.4. Exclusion of Particular Information

No data from the previous defined analysis set are excluded from the analysis except those defined in chapter 5.5, if applicable.

### 12.5. Descriptive Analyses

If applicable, mean and median survival times are presented by using the Kaplan-Meier estimates. Kaplan-Meier survival figures are presented for illustration.

Other descriptive data will be presented via tables as specified in chapter 5.1.

### 12.6. Hypotheses & Statistical Tests

#### CIP Chapter 7.3 Secondary hypotheses

*The objective to show that arrhythmias requiring guideline-recommended therapy will be detected earlier in the BioMonitor group will be formally tested similarly to the primary hypothesis. The HR is defined as the rate of the BioMonitor group divided by the rate of the control group.*

*H0: Null hypothesis:  $H_0 : HR \leq 1$  which means that monitoring patients of the BioMonitor group will not lead to a shorter time to first arrhythmia that requires guideline-recommended therapy, in the BioMonitor group compared to the control group.*

*HA: Alternative hypothesis:  $H_A : HR > 1$  which means that monitoring patients of the BioMonitor group will lead to a shorter time to first arrhythmia that requires guideline-recommended therapy compared to the control group.*

The hazard ratio for the BioMonitor versus control group including 95%CI is calculated with the Cox regression model. In case of doubt about the validity of the Cox model, the assumption of proportional hazards is checked graphically by log-minus-log survival versus log-time plots.

## 13. Other sec. EP: Time to all-cause death or heart transpl.

### 13.1. Analysis set

This endpoint is analyzed exclusively for the final statistical analysis report based on the ITT analysis set.

### 13.2. Variables

*CIP Chapter 8.3.3.1. Time to death from any cause or heart transplantation*

*Assessment of the time from randomization to death for any reason or heart transplantation during the clinical investigation.*

Data file: Identifier patient_ display_id_full	Notes	Variable name	Variable label	Variable level	Nominal values
data_SAR	descr.	death_htx_ITT_SAR 	Death or heart transplantation ITT	nominal	Yes / No
data_SAR	descr.	days_effrand_to_term_ ITT_SAR 	Days from effective randomization to termination ITT	scale	n.a.

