**8.3.3.1 Time to death from any cause or heart transplantation**

Assessment of the time from randomization to death for any reason or heart transplantation during the clinical investigation.

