#### 8.9.4.2 Patient death

In the event of subject death during study participation, personnel at the investigational site are requested to notify BIOTRONIK immediately by completing an adverse event eCRF and a study termination eCRF.

The following information will be required for any subject death in addition to the AE eCRF:

- Death certificate or death report, signed by the investigator, that includes:
  - Date of death
  - Primary cause of death
  - Any other circumstances surrounding the death
  - Whether death was device or procedure related if applicable

Whenever possible, devices that are explanted must be returned to BIOTRONIK for analysis.

All cases of patient death will be adjudicated by the EAEC.

In the event of a cardiac transplantation (HTX), the patient's participation in the study will be terminated. If the patient did not yet have a primary endpoint, the admission for the HTX procedure will be evaluated as the death of the patient and thus fulfils the criteria for a primary endpoint. HTX will also be contribute to the endpoints of all-cause mortality and cardiovascular mortality. Secondary endpoints such as the time to first arrhythmia can be assumed to differ significantly between post-HTX and post-MI patients and should thus not be pooled for analysis.

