## 6.8. Termination Date (= censoring date for the final ITT analyses)

### CIP chapter 8.9.5 Point of enrollment and study termination

...

*Regular point of termination for the individual patient is the respective date of the final study termination visit.*

*For all non-regular study terminations, the following rules apply:*

- *In case of patient death, the date of study termination is the date of death.*
- *In case of HTX, the discharge date from the HTX procedure's hospitalization is the date of study termination.*
- *In case of withdrawal of consent, the date of study termination is the date of withdrawal of consent.*
- *If patient is lost to follow-up, the date of termination is the date of last contact of the investigator or of the CRO that collects AEs. Data from the HMSC will not be used to ascertain the vital status of patients for any primary analysis because this might introduce a bias in favor of the BM arm.*
- *If patient is defined as drop-out patient for any other reason, the date of study termination is the date on which the reason for the drop-out became effective, i.e. the date on which a violation of inclusion criteria was discovered, or on which the investigator excluded the patient for safety reasons.*

The variable term\_date compromises the above definition, which is an instruction for the investigator how to report the termination date. The variable term\_date will be checked during monitoring and during the blind review of the data before CDMS freeze or closure.

All remaining patients are terminated when the formal study termination is announced. Therefore, no individual study termination can be later than the formal study termination.

Data file: Identifier	Variable name	Variable label	Variable level	Nominal values
patient_display_id_full				
study_termination	term_date	Date of study termination	date	n.a.
study_termination	regular_yn	regular study termination	nominal	Yes / No

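### As labelled, SAP 13.2 and 14.2 date a heart transplant at discharge from the transplant stay, which is later than the event the protocol defines

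*SAP*

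**What the plan says.** **Endpoint definitions.** Protocol 8.3.3.1 reads: "Assessment of the time from randomization to death for any reason or heart transplantation during the clinical investigation". Protocol 8.3.3.2 does the same for cardiovascular death or transplantation.

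**Transplant rule.** Where no MACE has occurred before, protocol 8.9.4.2 gives this rule: "the admission for the HTX procedure will be evaluated as the death of the patient and thus fulfils the criteria for a primary endpoint". On mortality it adds: "HTX will also be contribute to the endpoints of all-cause mortality and cardiovascular mortality". For secondary endpoints such as time to first arrhythmia, it says they "can be assumed to differ significantly between post-HTX and post-MI patients and should thus not be pooled for analysis".

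**Termination rule.** SAP 6.8, repeating protocol 8.9.5, says: "In case of HTX, the discharge date from the HTX procedure's hospitalization is the date of study termination". For a patient who dies, termination is the date of death. SAP 6.8 describes the rule set as one "which is an instruction for the investigator how to report the termination date", so `term_date` should follow it.

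**Time variable.** SAP 13.2 and 14.2 each list one event indicator and the same time variable, `days_effrand_to_term_ITT_SAR`, labelled "Days from effective randomization to termination ITT". Neither lists an event date. SAP 10 derives an adjudicated HTX date, `date_htx_2of3chair_SAR`, but neither section names it.

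**The concern.** Using termination as the event time is a sound shortcut for deaths. It fails for transplantation, the component added to both endpoints, because termination then falls at the end of the hospital stay.

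The rest of the SAP does not take this shortcut. The hospitalization endpoints in SAP 15 to 20 are labelled as time to the first event or, failing that, termination. The primary endpoint has its own adjudicated event date. The same transplant could therefore carry one date in MACE and a later one in all-cause and cardiovascular mortality.

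A related, lesser matter concerns SAP 12 (first arrhythmia needing guideline-recommended therapy), SAP 21 (first arrhythmia) and SAP 23 (first therapy). As labelled, these also run to termination, so a transplanted patient with no earlier event stays at risk through the postoperative stay. That does not sit well with the protocol's statement that post-HTX and post-MI data should not be pooled. SAP 12 carries the only secondary hypothesis that is formally tested.

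**Working it through.** The plan states no figure on this point, so there is nothing to reproduce. The check sets the date rules side by side.

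**1. Event date and analysis time by type of patient (SAP 13; SAP 14 with cardiovascular death)**

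| Patient | Event date in the protocol | Time in SAP 13.2/14.2 as labelled | Gap |
|---|---|---|---|
| Dies, no transplant | Death | Termination = death | 0 |
| Transplanted, discharged alive | Transplantation (8.3.3.1–2) or HTX admission (8.9.4.2) | Termination = discharge | Discharge minus event date |
| Transplanted, dies in that stay | As above | End of the stay, by the death rule or the discharge rule | End of stay minus event date |
| No event | None; censored at termination | Termination | 0 |

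Only transplanted patients are affected. Discharge follows both the admission and the operation, so the sign of the gap does not depend on which one is the event.

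**2. Size for one patient (invented record)**

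Admission day 400, operation day 430, discharge day 470.

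- If the event is the admission: 470 − 400 = 70 days late.
- If the event is the operation: 470 − 430 = 40 days late.

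**3. Size for the comparison**

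The documents give neither a number of transplants nor a length of stay. With LVEF above 35% at entry, I assume 0 to 3 transplants in the trial and stays of 3 to 12 weeks.

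To bound the effect on the hazard ratio, data were simulated under deliberately unfavourable assumptions: 1000 patients, an event rate of 3% per year, 180 to 2200 days of follow-up, and 1 to 10 transplants all in one arm, each dated 14, 30 or 90 days late. There were 40 data sets per setting. The measure is the Cox hazard ratio timed to discharge divided by the hazard ratio timed to the earlier date.

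- All settings: mean ratio 0.9986 to 1.0000; single data sets 0.976 to 1.011.
- 3 transplants, 90 days late: mean 0.9995; single data sets 0.998 to 1.004.

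The number of death-or-HTX events is the same under either timing.

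**4. SAP 12, 21 and 23**

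Each transplant can add at most one first event per endpoint, and only if the patient had none before.

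- SAP 12 requires the arrhythmia to need a guideline-recommended change of therapy (`arrchange_yn`).
- SAP 23 leaves out therapy changes prescribed outside the investigational site.
- SAP 21 asks only for a documented arrhythmia, so it is the most open of the three.

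Under the assumption above this means 0 to 3 possible events per endpoint at the very most.

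**The case against.** **The derivations are not visible.** The SAP puts its derivation rules in footnotes. The text of footnotes 86–87 and 89–90 (the two endpoints) and 57–58 (the HTX flag and date) could not be read in the copy reviewed. A footnote may already use the HTX date, and unreadable text is not a gap in the plan. This stands as a limit on certainty. Against it, the variable's name and label both say termination, and the same variable serves both endpoints. If a footnote does use the HTX date, the name and label are what need correcting.

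**The admission rule is explicit only for the primary endpoint.** A reader might infer that the protocol fixes the admission as the event in the mortality endpoints, so that the error is always the whole stay. The protocol does not say that. For mortality, 8.9.4.2 says only that HTX contributes, and 8.3.3.1–2 name the transplantation. This objection is right about the size of the gap but does not remove it.

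**The HTX date in SAP 10 is itself undefined.** Its visible label does not say whether it is the admission or the operation, and the date used for MACE is no clearer. This stands, and the fix has to settle it.

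**The consequence is negligible.** These are other secondary endpoints without pre-defined hypotheses, and few or no transplants are likely. That also stands. It bears on priority, not on whether the labelled rule matches the definition.

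**Conclusion.** The point holds as a small inconsistency. As labelled, SAP 13 and 14 date the transplant component later than the protocol's event on either reading, by up to the length of the stay. This is a stated rule that misdates one component rather than a missing detail, subject to the unread footnotes.

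The size rests on assumed numbers of transplants and lengths of stay. Under those assumptions the shift in the hazard ratio is far below anything that could alter interpretation. With no transplants it is zero.

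Two stronger conclusions are tempting and not supported:

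- **That the primary result or the mortality counts are wrong.** The primary endpoint has its own event date, and the same patients are events under either timing.
- **That postoperative arrhythmias will contaminate the arrhythmia endpoints.** The protocol says such data should not be pooled, which is weaker than a prohibition. The therapy-change condition in SAP 12 and the investigational-site restriction in SAP 23 narrow what can count. What remains is a possible handful of events, chiefly in SAP 21.

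**What to change.** - **SAP 13.2:** set the event time to the earlier of the date of death and `date_htx_2of3chair_SAR`. Use `term_date` only to censor patients with neither event.
- **SAP 14.2:** set the event time to the earlier of the date of cardiovascular death and the same HTX date. Use `term_date` only for censoring. In SAP 10 the cardiovascular-death date variable, `date_cvdeath_2of3chair_SAR`, carries the label of the HTX date; correct that label at the same time.
- **SAP 10:** state whether the HTX date is the admission or the operation, and make it consistent with the date used for the primary endpoint.
- **SAP 12, 21 and 23:** censor transplanted patients at that same HTX date.
- If the footnotes already do this, rename and relabel the time variable in 13.2 and 14.2.

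The cost is about one line per derivation. An adjudicated HTX date is already derived, so no new data collection is indicated, although its meaning has to be confirmed.

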### 13.3. Treatment of Missing and Spurious Data

Spurious data, which were not clarified by the query process before CDMS closure, are indicated. If appropriate, descriptive and inferential analyses are performed both with /without such data.

#### 13.1. Exclusion of Particular Information

No data from the previous defined analysis set are excluded from the analysis except those defined in chapter 5.5, if applicable.

#### 13.2. Descriptive Analyses

If applicable, mean and median survival times are presented by using the Kaplan-Meier estimates. Kaplan-Meier survival figures are presented for illustration.

Other descriptive data will be presented via tables as specified in chapter 5.1.

#### 13.1. Hypotheses & Statistical Tests

The hazard ratio for the BioMonitor versus control group including 95%CI is calculated with the Cox regression model. In case of doubt about the validity of the Cox model, the assumption of proportional hazards is checked graphically by log-minus-log survival versus log-time plots.

## 14. Other sec. EP: Time to CV death or heart transplantation

### 14.1. Analysis set

This endpoint is analyzed exclusively for the final statistical analysis report based on the ITT analysis set.

### 14.2. Variables

#### *CIP Chapter 8.3.3.2 Time to cardiovascular death or heart transplantation*

*Assessment of the time from randomization to cardiovascular death or heart transplantation during the clinical investigation. A specified endpoint definition will be given by the members of the EAEC ...*

Data file: Identifier	Notes	Variable name	Variable label	Variable level	Nominal values
patient_display_id_full					
data_SAR	descr.	cvdeath_htx_ITT_SAR 	CV death or heart transplantation ITT	nominal	Yes / No
data_SAR	descr.	days_effrand_to_term_ITT_SAR 	Days from effective randomization to termination ITT	scale	n.a.

### 14.3. Treatment of Missing and Spurious Data

Spurious data, which were not clarified by the query process before CDMS closure, are indicated. If appropriate, descriptive and inferential analyses are performed both with /without such data.

### 14.4. Exclusion of Particular Information

No data from the previous defined analysis set are excluded from the analysis except those defined in chapter 5.5, if applicable.

### 14.5. Descriptive Analyses

If applicable, mean and median survival times are presented by using the Kaplan-Meier estimates. Kaplan-Meier survival figures are presented for illustration.

Other descriptive data will be presented via tables as specified in chapter 5.1.

### 14.6. Hypotheses & Statistical Tests

Differences of the survival curves BioMonitor versus control group are tested for statistical inference with the log-rank test.

The hazard ratio for the BioMonitor versus control group including 95%CI is calculated with the Cox regression model. In case of doubt about the validity of the Cox model, the assumption of proportional hazards is checked graphically by log-minus-log survival versus log-time plots.

## 15. Other sec. EP: Time to 1st worsening of the patient status due to heart failure ...

### 15.1. Analysis set

This endpoint is analyzed exclusively for the final statistical analysis report based on the ITT analysis set.

### 15.2. Variables

*CIP Chapter 8.3.3.3 Time to first worsening of the patient status due to heart failure requiring hospitalization or urgent visit*

*Assessment of the time from randomization to first hospitalization or urgent visit for worsening of the patient status due to heart failure, or death due to heart failure. A specified endpoint definition will be given by the members of the EAEC and documented in the charter agreement*

Data file: Identifier	Notes	Variable name	Variable label	Variable level	Nominal values
patient_display_id_full					
data_SAR	descr.	any_hf_ITT_SAR 	Any hospitalization or urgent visit for worsening of the patient status due to heart failure, or death due to heart failure after effective randomization ITT	nominal	Yes / No
data_SAR	No report	date_1hf_ITT_SAR 	Date of 1st hospitalization or urgent visit for worsening of the patient status due to heart failure, or death due to heart failure after effective randomization ITT	date	n.a.
data_SAR	descr.	days_effrand_to_1hf_ITT_SAR 	Days from effective randomization to 1st t hospitalization or urgent visit for worsening of the patient status due to heart failure, or death due to heart failure or termination ITT	scale	n.a.

### **15.3. Treatment of Missing and Spurious Data**

Spurious data, which were not clarified by the query process before CDMS closure, are indicated. If appropriate, descriptive and inferential analyses are performed both with /without such data.

#### **15.1. Exclusion of Particular Information**

No data from the previous defined analysis set are excluded from the analysis except those defined in chapter 5.5, if applicable.

#### **15.2. Descriptive Analyses**

If applicable, mean and median survival times are presented by using the Kaplan-Meier estimates. Kaplan-Meier survival figures are presented for illustration.

Other descriptive data will be presented via tables as specified in chapter 5.1.

#### **15.3. Hypotheses & Statistical Tests**

Differences of the survival curves BioMonitor versus control group are tested for statistical inference with the log-rank test.

The hazard ratio for the BioMonitor versus control group including 95%CI is calculated with the Cox regression model. In case of doubt about the validity of the Cox model, the assumption of proportional hazards is checked graphically by log-minus-log survival versus log-time plots.

## 16. Other sec. EP: Time to 1st hosp. resulting from an arrhythmia

### 16.1. Analysis set

This endpoint is analyzed exclusively for the final statistical analysis report based on the ITT analysis set.

### 16.2. Variables

*CIP chapter 8.3.3.4. Time to first hospitalization resulting from an arrhythmia*

*Assessment of the time from randomization to the first hospitalization resulting from an arrhythmia or death resulting from arrhythmia. A specified endpoint definition will be given by the members of the EAEC and documented in the charter agreement.*

Data file: Identifier patient_ display_id_full	Notes	Variable name	Variable label	Variable level	Nominal values
data_SAR	descr.	any_arr_ITT_SAR 	Any hospitalization resulting from an arrhythmia or death resulting from arrhythmia after effective randomization ITT	nominal	Yes / No
data_SAR	No report	date_1arr_ITT_SAR 	Date of 1st hospitalization resulting from an arrhythmia or death resulting from arrhythmia after effective randomization ITT	date	n.a.
data_SAR	descr.	days_effrand_to_1arr_ITT_SAR 	Days from effective randomization to 1st hospitalization resulting from an arrhythmia or death resulting from arrhythmia or termination ITT	scale	n.a.

### **16.3. Treatment of Missing and Spurious Data**

Spurious data, which were not clarified by the query process before CDMS closure, are indicated. If appropriate, descriptive and inferential analyses are performed both with /without such data.

#### **16.1. Exclusion of Particular Information**

No data from the previous defined analysis set are excluded from the analysis except those defined in chapter 5.5, if applicable.

#### **16.2. Descriptive Analyses**

If applicable, mean and median survival times are presented by using the Kaplan-Meier estimates. Kaplan-Meier survival figures are presented for illustration.

Other descriptive data will be presented via tables as specified in chapter 5.1.

#### **16.3. Hypotheses & Statistical Tests**

Differences of the survival curves BioMonitor versus control group are tested for statistical inference with the log-rank test.

The hazard ratio for the BioMonitor versus control group including 95%CI is calculated with the Cox regression model. In case of doubt about the validity of the Cox model, the assumption of proportional hazards is checked graphically by log-minus-log survival versus log-time plots.

## 17. Other sec. EP: Time to 1st hosp. resulting from acute coronary syndrome

### 17.1. Analysis set

This endpoint is analyzed exclusively for the final statistical analysis report based on the ITT analysis set.

### 17.2. Variables

#### *CIP cChapter 8.3.3.5. Time to first hospitalization resulting from acute coronary syndrome*

*Assessment of the time from randomization to the first hospitalization resulting from acute coronary syndrome or death resulting from acute coronary syndrome. A specified endpoint definition will be given by the members of the EAEC and documented in the charter agreement.*

Data file: Identifier patient_ display_id_full	Notes	Variable name	Variable label	Variable level	Nominal values
data_SAR	descr.	any_acs_ITT_SAR 	Any hospitalization resulting from acute coronary syndrome or death resulting from acute coronary syndrome after effective randomization ITT	nominal	Yes / No
data_SAR	No report	date_1acs_ITT_SAR 	Date of 1st hospitalization resulting from acute coronary syndrome or death resulting from acute coronary syndrome after effective randomization ITT	date	n.a.
data_SAR	descr.	days_effrand_to_1acs_ITT_SAR 	Days from effective randomization to 1st hospitalization resulting from acute coronary syndrome or death resulting from acute coronary syndrome or termination ITT	scale	n.a.

